14.1. Institutional Review Board/Independent Ethics Committee

The [REDACTED] will be the IRB of record for this study. The [REDACTED] has oversight of 10 convened IRBs, of which 8 meet monthly. The [REDACTED] holds a Federal-Wide Assurance [REDACTED]

from the Department of Health and Human Services (DHHS) Office for Human Research Protections (OHRP) that allows us to review and approve human subject procedures through our IRB committees. These committees are also registered with OHRP for both DHHS and Food and Drug Administration-regulated research. The FWA requires IRB review for all studies conducted by Duke that involve human subjects, regardless of the funding source.

14.2. Informed Consent

An electronic consent document will be provided by site research staff via website link. The consent document will provide information about the study and instruct participants that they may contact their study doctor and/or the IRB should they have any questions about the study. Site research staff are responsible for providing the contact information along with the link to the consent form. Participants will be asked to read this information, and they will be given the option to agree or not agree to continue with the PPI survey.

1. STUDY DESIGN OVERVIEW

The primary objective of this study is to quantify patients' willingness to accept tradeoffs among pacemaker device features. To achieve the study objective, the [REDACTED]

[REDACTED] at Duke Clinical Research Institute (DCRI) has developed a discrete-choice experiment (DCE) survey instrument that adheres with guidance issued by Food and Drug Administration (FDA) in August 2016 and best practices identified by stated-preference experts (Bridges et al., 2011; Reed Johnson et al., 2013).

In the DCE, respondents are asked to select their preferred treatment options in a series of experimentally controlled pairs of hypothetical devices. The devices are defined by pacemaker type (pacemaker with leads, leadless pacemaker-removable, and leadless pacemaker- not removable), years of battery life (15 years, 12 years, 8 years, 5 years), years since government approval (10 years, 2 years), discomfort for 6 months (no discomfort, discomfort), and device-related risks of adverse events (risk of infection requiring removal and antibiotics and risk of complication requiring an operation). To gain insights about device features that are inextricably linked to a specific type of pacemaker that were not amenable to inclusion in a DCE, a ranking exercise was designed to elicit information on participants' relative concern for these device features (insertion procedure, where the device is implanted/resides in the body, the need for leads, whether the device is externally visible, and duration of activity restrictions after the device is implanted).

To prepare respondents for the DCE choice questions, the survey instrument includes carefully worded descriptions of all attributes, comprehension questions, a tutorial for probabilistic attributes, and simplified practice choice questions. Development and pretesting the survey instrument have been described in a separate memo.

Abbott will take primary responsibility for working with operational teams and Investigational Device Exemption (IDE) study sites to develop plans for recruitment and assist with their dissemination to study sites. DCRI will review site recruitment and training materials developed by Abbott for the patient preference study. Respondents eligible to participate in the online patient-preference study will be recruited from all adult patients who are referred to a study site for evaluation for a pacemaker or with a known indication for a de-novo pacemaker. Study sites will track which respondents agreed to be screened for the IDE trial and which respondents ultimately enrolled in the IDE trial.

This document provides details about the DCE and its experimental design, the ranking exercise, and the plan for statistical analysis.

1.1. Discrete-Choice Experiment

1.1.1. Attributes and Levels

[figure not shown]
At the core of every discrete-choice study is a set of treatment features or attributes that define the constructed treatments evaluated in the study. In a series of choice questions, respondents choose between two or more of these constructed treatments, where the levels of benefit and risk attributes are varied experimentally. The attributes and levels included in this study are shown in Table 1, and an example choice question is shown in Figure 1.

Table 1. Study Attributes and Levels

Attributes	Levels
Pacemaker type	
 • Pacemaker with leads • Leadless pacemaker removable • Leadless pacemaker not removable
Years of battery life	
 • 5 years • 8 years • 12 years • 15 years
Years since government approval	
 • 2 years • 10 years
Discomfort for 6 months	
 • No discomfort • Discomfort
Chance of complication requiring an operation	
 • 1% • 5% • 10% or 20%*
Risk of infection requiring removal and antibiotics	
 • 1% • 5% • 10% or 20%*

*Scope test – each respondent will be assigned to either 10% or 20% as the highest risk level for infection and complication risks.

As shown in Figure 1, each of the choice questions in this study consists of a choice between two pacemaker options in which attribute levels vary according to the experimental design.

Figure 1. Example Choice Question

1.1.2. Scope Test

As indicated in Table 1, each respondent will be randomized into a study arm in which 10% or 20% is shown as the highest risk level for chance of complication requiring an operation and chance of infection requiring removal and antibiotics. A scope test is designed to evaluate whether respondents are responsive to the magnitude of risk levels shown rather than rescaling the levels as ordinal measures (e.g. low, medium, high). Thus, we hypothesize that respondents randomized to the high-risk arm (i.e. 20% shown as the highest risk level) will have more negative preferences for the highest risk levels compared to respondents randomized to the low-risk arm (i.e. 10% shown as the highest risk levels). The scope test also allows us to evaluate whether the highest risk levels shown differentially impact preferences for the lower risk levels (i.e. 1% and 5%) shown in the low-risk and high-risk arms. We hypothesize that respondents' preferences in the low-risk and high-risk arms will not differ for the 1% and 5% risk levels for either adverse-event attribute.

1.1.3. Experimental Design

The experimental design determines the combinations of attribute levels that define each hypothetical pacemaker profile and the pairs of hypothetical profiles that will populate the choice questions in the DCE section of the survey.

The experimental design algorithms are designed to maximize the statistical efficiency (D-optimality¹) of the choice questions. The efficiency of an experimental design is partly related to level balance—the number of times that each level and pair of levels is shown in the design.

By identifying potential designs based on D-optimality, we can control the statistical properties of the complete design. However, blocking, incomplete responses, and potential cognitive factors (e.g., unaccounted interaction effects, simplifying heuristics, etc.) can affect our ability to identify all preference parameters.

The smallest feasible experimental design requires as many questions as preference parameters to be estimated (i.e. total number of levels less total number of attributes). Accounting for the number of attribute levels (two 2-level attributes, three 3-level attributes, and one 4-level attribute) and assuming that all attribute-level variables will be effect-coded, this implies a design with at least 11 choice questions. However, to cover more unique combinations of attribute levels (Janssen, Hauber, & Bridges, 2018) within and across pacemaker alternatives, we used algorithms by Kuhfeld in SAS (Kuhfeld, 2010) to generate orthogonal experimental designs from the full factorial design of 768 profile pairs. Efficient designs suggested by the algorithms included 48 and 96 profile pairs.

[figure not shown]
Our pretest interviews demonstrated that respondents were able to assess at least 8 choice questions without becoming overly fatigued. Considering the expected sample size of 300 and the plan to generate multiple sequences of choice questions within blocks for implementation in Sawtooth, we chose to generate a design with 48 profile pairs, split into 6 blocks of 8 choice questions. We generated several designs with 48 pairs of hypothetical pacemakers. No restrictions were implemented in the design, thus all levels across attributes could be combined to represent hypothetical pacemaker alternatives. The resulting designs had very similar statistical efficiency. DCRI chose a design with acceptable balance between levels.

¹ D-optimality is a criterion that supports the maximization D-efficiency in an experimental design given the number of attributes, attribute levels, choice questions, and design restrictions. D-optimality is used when orthogonality cannot be achieved in a design given the number of choice questions or the restrictions in the design. At a D-optimal point, the design has maximized the determinant of the information from the choice questions, and minimized the expected variance for the expected preference estimates.

Because Sawtooth Software does not allow for automated randomization of the sequence of questions within blocks, we took steps to avoid order effects that could potentially occur when individuals complete the same sets of questions in the same order. For each of the 6 blocks, we randomly ordered each set of 8 questions. When the survey is administered, each participant will be assigned to complete one of 48 sets of 8 questions so that all blocks are approximately equally represented.

To extract more choice information from individual respondents, we also will ask survey respondents whether they are willing to complete 4 additional choice questions for a total of 12 questions. To construct choice sets for the additional 4 choice questions, we generated a 24-question experimental design, again with no restrictions, and divided the design into 6 blocks of 4 questions. Each of these 6 blocks were replicated 4 times each with different question sequences. Respondents who are willing to complete 4 additional choice questions will be assigned to one of 24 sets of 4 questions. In total, the design includes 8 unique sequences for each of the 6 blocks in the 48-question design and 4 unique sequences for each of the 6 blocks in the additional 24-question design. To implement the scope test, we duplicated and recoded the risk levels such that either 10% or 20% would be shown as the highest risk levels. Figure 2 provides an overview of the experimental designs for the study.

Figure 2. Experimental Design

*not representative of actual sequences or block assignment

1.1.4. Validity Tests and Quality Control

Specific modifications to the D-optimal design include validity tests to characterize the overall quality of the preference data collected in the study. Validity tests provide the opportunity to more closely evaluate responses that do not meet a minimum level of consistency with the economic principles underlying DCEs. However, the results must be interpreted carefully. Apparent inconsistencies could be accurate indicators of patient preferences or results of reasonable assumptions not accounted for in the study design (Janssen et al., 2018).

The study experimental design is expected to allow between-question consistency tests. These tests evaluate whether respondents who make choices that imply specific preferences also make choices that are consistent or inconsistent with such preferences elsewhere in the survey. Since these inconsistencies are correlated with measurement error, they can signal problems with the magnitude of the errors in the final preference estimates.

An additional indicator of internal validity is respondents' performance on comprehension questions included in the survey instrument after describing each study attribute, after the risk-grid tutorial, and after the practice-choice questions. These questions will be used to flag any respondents whose responses indicate that they may not completely understand the study attributes or question layout or may be generally inattentive to the survey content.

1.2. Ranking Question

To gain insights about device features that are inextricably linked to a specific type of pacemaker and thereby not amenable to inclusion in a DCE, a ranking exercise was designed to elicit information on participants' relative concern for these device features. These features include the insertion procedure, where the device is implanted/resides in the body, the need for leads, whether the device is externally visible, and duration of activity restrictions after the device is implanted (Table 2).

In a ranking exercise, it is important that all features included in the exercise are either positive or negative. Because the options pertaining to the insertion procedure, presence of leads and location are not clearly positive or negative, survey respondents are first asked to indicate which specific aspect of a pacemaker attribute is of greater concern for these three features (see first three rows of Table 2 below). For example, with regard to leads, respondents could choose "having a pacemaker without leads" or "having a pacemaker with leads", as shown in Table 2. The chosen feature of greater concern is then transferred to the ranking exercise so that all features shown in the ranking exercise represent negative aspects of pacemakers from the patient perspective.

Table 2. Items in the Ranking Exercise

Insertion procedure

• Pacemaker inserted through cut in skin on the chest• Pacemaker inserted using tube through the groin
Leads

• Having a pacemaker with leads• Having a pacemaker without leads
Pacemaker location

• Having a pacemaker placed under the skin on the chest• Having a pacemaker attached to the walls inside the heart
No heavy lifting is allowed for 6 weeks (versus limited activity for 2 weeks)
Scar on chest (versus no scar)
Lump on chest (versus no lump)

2. STATISTICAL ANALYSIS

2.1. Data Summary

Descriptive statistics will be generated to describe the study sample. We will summarize the responses to each of the questions on respondents' demographic and socioeconomic characteristics and experience with heart problems and heart problem treatments, as well as questions testing whether respondents comprehended the information presented to them in the survey instrument. Summary statistics will be calculated based on the number of valid responses to the question and exclusive of any missing data. For categorical questions, we will compute the number and percentage of the sample providing each response. Continuous response questions will be summarized by the mean, standard deviation, minimum, and maximum values. [REDACTED]

[REDACTED]
[REDACTED]
[REDACTED] *P*-values will be computed using Pearson's chi-square test for categorical variables or Student's t-test for continuous variables.

2.2. Discrete-Choice experiment

Discrete-choice experiments generate complex cross-section/time-series choice data for each respondent. These data include a dichotomous dependent variable and are analyzed using advanced statistical methods. The basis for the analysis is the model specification assumed when generating the experimental design prior to survey implementation. That specification considers a categorical main-effects model for all study attributes. However, the specification assumed in the experimental design takes into account only statistical considerations. The statistical analysis of choices will provide a measure of the impact of changes in the attribute levels on the likelihood that treatments are selected by respondents, also referred to as attribute-level preference weights.

Respondents' reactions to the stimuli in DCE questions generally involve a complex decision process, and the final model specification must account for the pattern of choices as observed in the data set. For this reason, it is not advisable to pre-specify a final model specification before analyzing preference data. This statistical analysis plan lays out the initial analyses that will be conducted to assess the quality of the data and describes exploratory analysis strategies that will inform the final model specification.

The design and study specifications have been developed to support a robust analysis that includes estimates of relative preference weights and maximum-acceptable risk (MAR). In addition, the data will support more advanced analytic strategies to understand preference heterogeneity among respondents with different demographic, clinical, and treatment characteristics.

2.3. Evaluation of Data Quality and Its Impact on Treatment Preferences

The survey included 11 comprehension questions that can be used to identify any respondent who may not completely understand the study attributes or question layout or may be generally inattentive to the survey content. Also, the design of the DCE allows for several tests of internal validity (Johnson, Yang, & Reed, 2019). We describe below each test that will be used initially to evaluate data quality and then assess its effect on treatment preferences.

2.3.1. Respondents' Performance on Comprehension Questions

Respondents' performance on comprehension questions can be an indicator of internal validity. The questions will be used to identify any respondents whose responses indicate that they may not completely have understood the study attributes or question layout.

Along with the time spent completing the survey, we will use the information to determine whether some respondents should be excluded from the final analysis. In addition, we will assess whether respondents with more incorrect responses to comprehension questions exhibit statistically significantly different preference estimates compared to those who answered more comprehension questions correctly.

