This recruitment approach affords preference measurement among a broader set of patients representing people in the US who may soon have to make a real-world decision about choosing de-novo pacemaker. Additionally, it will allow for a comparison of patient preferences between two groups. The first group includes: 1) individuals who are not candidates for a dual-chamber pacemaker; 2) not asked to be screened for participation in the IDE trial; or 3) asked to be screened for the IDE trial and decline (verbal or written) (Group 1 in Figure 1). The second group includes all patients who agree (verbal or in writing) to be screened in the IDE trial, including individuals who are later found to be ineligible to participate and individuals who are eligible but ultimately choose do not consent and enroll in the ICE trial (Group 2 in Figure 1). Comparisons between these groups will test whether individuals who initially agree to consider participating in an investigational device trial are less risk averse than individuals who do not. For patients who verbally consent to be screened for participation in the IDE trial, a case report form will be used to record PPI passcodes, whether the patient met eligibility criteria, and whether the patient ultimately enrolled in the IDE trial. Thus, patients with passcodes in the trial data will be used to identify patients in Group 2. All other PPI respondents will be included in Group 1.

Abbott will take primary responsibility for working with operational teams and study sites to develop training materials for recruitment and assist with their dissemination to study sites.

[figure not shown]
8. Sample Size

The target sample size is a minimum of 300 patients from US IDE sites. For maximum statistical power, nearly equal enrollment in Group 1 and Group 2 (n=150 each) is ideal. However, as it is not known beforehand who will ultimately participate in the IDE trial and who will not, a specific number of individuals in each group cannot be guaranteed.

Formal sample size calculations for DCEs are not possible without priors for respondents' preferences. In addition, the information needed to identify all relevant preference weights can vary significantly across instruments and populations. [REDACTED]

[REDACTED]

[REDACTED]

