2.4.2. Scope Test

As explained in Section 1.1.2, we embedded a scope test to evaluate whether respondents are sensitive to the actual risk levels shown. Respondents assigned to the low-risk arm will see maximum risk levels of 10% for both the infection risk and complication risk attributes. Respondents assigned to the high-risk arm will see maximum risk levels of 20% for both risk attributes. If respondents systematically recode the risk levels qualitatively (for example, as low, medium, and high), the scope test would show that preference estimates are not sensitive to the overall risk range (i.e., the relative weight for the 10% level in the low-risk arm is not different than the relative weight for the 20% risk level in the high-risk arm). Because the other two levels in the experimental design overlap between arms, we can also assess whether the overall preference for the 1% and 5% risk levels are influenced by the maximum risk levels that respondents evaluate.

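### SAP 2.3.1 tests whether poor comprehenders have different preference weights, but no readable text separates noisier answering (logit scale) from different preferences

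*SAP*

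**What the plan says.** SAP 2.3 records that "The survey included 11 comprehension questions" and presents them as a way to find people who did not follow the attributes or layout, or who were not paying attention. SAP 2.3.1 (the subsection on comprehension performance; the number is used twice) then makes two separate uses of the answers.

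- With completion time, "we will use the information to determine whether some respondents should be excluded from the final analysis".
- In a further sentence, "we will assess whether respondents with more incorrect responses to comprehension questions exhibit statistically significantly different preference estimates" relative to those with more correct answers.

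For the second use, the section gives no model, test statistic, significance level, cut-point on the 11 items or scale parameter.

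Elsewhere in the readable text:

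- SAP 2.4.1 starts from an effect-coded conditional logit and concedes that it simplifies the error terms. SAP 2.4.4 plans a mixed logit with correlated normal random parameters for the equivalence values. Protocol 11.3 defines the estimates as log-odds weights.
- SAP 1.1.4 says of between-question consistency tests: "Since these inconsistencies are correlated with measurement error", they can signal error problems in the final estimates. That sentence concerns a different validity check, but it shows that the authors expect poor-quality answering to carry more error.
- SAP 2.4.2 describes insensitivity to risk range as the case where "the relative weight for the 10% level in the low-risk arm is not different than the relative weight for the 20% risk level" in the other arm.

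The bodies of SAP 2.4.3 and 2.4.5 are not readable. The reference list holds a paper on mixed logit with panel and scale effects that no readable text cites.

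**The concern.** A logit model does not estimate preferences on their own. It estimates preferences multiplied by a scale factor that shrinks as response error grows. Two groups that make the same trade-offs but answer with different amounts of noise will have different log-odds weights, all shrunk in the same proportion.

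The comparison in 2.3.1 splits the sample on a marker chosen because it should pick out inattentive, hence noisier, respondents. A direct test of their weights against everyone else's tests noise and preference together. A significant result could be reported as poor comprehenders wanting different things from a pacemaker when they only answered less consistently. The first reading questions whose preferences the sample represents; the second describes data quality.

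The scope test has a milder form of the problem. The 10% and 20% weights always come from different respondents, so a scale gap between arms would enter the comparison directly.

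**Working it through.** **The plan's own figure.** SAP 1.1.3 counts the preference parameters as levels minus attributes. With two 2-level, three 3-level and one 4-level attribute: 2(2−1) + 3(3−1) + 1(4−1) = 2 + 6 + 3 = 11. This reproduces the stated 11 and fixes the degrees of freedom below. The documents give no power, significance level or group size for the comprehension comparison.

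**Why scale matters.** For a pair of profiles A and B, P(choose A) = 1 / (1 + exp[−s·(x_A − x_B)′β]). Only the product sβ can be estimated. If both groups share β and the noisier group has scale s < 1, its weights are sβ. Ratios are unaffected: (sβ_j)/(sβ_k) = β_j/β_k. Trade-off quantities therefore survive a scale difference and raw weights do not.

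**Inputs from the documents.**
- Sample size: "The target sample size is a minimum of 300 patients from US IDE sites" (Protocol 8).
- Design: 48 pairs "split into 6 blocks of 8 choice questions" (SAP 1.1.3). The 4 optional questions were ignored.
- 11 effect-coded parameters, conditional logit (SAP 1.1.3, 2.4.1).

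**Assumptions not in the documents.** A joint likelihood-ratio test at 5%; two sets of true weights (the smaller set is 0.6 times the larger); the group splits; the scale ratios; no preference heterogeneity within groups; a random-search design in place of the unpublished one. 400 data sets per cell, so the Monte Carlo standard error near 5% is √(0.05 × 0.95/400) ≈ 1.1 points.

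**Two tests on data with identical true preferences.**
- Without scale: separate weights (22 parameters) against pooled weights (11), so 11 df.
- With scale: separate weights (22) against common weights plus one relative scale (12), so 10 df.

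False rejection without a scale term, by scale ratio of the noisier group:

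| Weights | Split | 1 | 0.8 | 0.67 | 0.5 | 0.33 |
|---|---|---|---|---|---|---|
| larger | 150:150 | 6.5% | 24% | 73% | 99% | 100% |
| larger | 225:75 | 4% | 20% | 57% | 95% | 100% |
| larger | 270:30 | 7% | 15% | 26% | 65% | 96% |
| smaller | 150:150 | 3% | 12% | 35% | 80% | 98% |
| smaller | 225:75 | 3% | 12% | 26% | 59% | 95% |
| smaller | 270:30 | 7% | 8% | 12% | 33% | 61% |

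With the scale term, rejection is about 3% to 8% in every cell, whatever the ratio.

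**Scope test, illustrative arithmetic.** Assume a disutility of 0.1 per percentage point measured from 1%. The 10% level then costs 0.1 × 9 = 0.9 and the 20% level 0.1 × 19 = 1.9, a true step of 1.00. If the 20% arm had scale 0.8, its weight would show as 1.9 × 0.8 = 1.52 and the step as 1.52 − 0.9 = 0.62. To hide the step entirely, the scale would have to fall to 0.9/1.9 = 0.47.

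**The case against.** The strongest reply is that the plan is silent on method rather than wrong. SAP 2.3.1 names no model, two modelling sections are blacked out, and a scale-effects paper in the references was presumably cited somewhere. A scale method may well exist. This stands as a limit on what can be asserted. It does not change the rules in 2.3.1 and 2.4.2, which show no redaction and speak of comparing estimates or weights directly. If the method exists, those sections need to point to it.

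Second, the size depends on assumptions. With a mild noise difference and few poor performers, rejection is 8% to 15%, against about 7% in the same split with no scale difference. This stands: the problem can occur but is not certain to.

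Third, 2.3 is a data-quality check, and shrunken weights are themselves a quality signal. True, but the check is worded as a test of different preferences and would be reported as one.

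Fourth, the scope arms are randomised (SAP 1.1.2), so a scale gap there could come only from the risk range shown or from chance. The planned comparison of the shared 1% and 5% levels also gives a partial check. This stands and makes the scope-test point a safeguard only.

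A reader might infer three further things that the documents do not support.
- That this comparison decides who is excluded. The exclusion sentence in 2.3.1 rests on comprehension answers and completion time, and nothing makes it depend on the test result.
- That the test in Protocol 7 of whether those agreeing to screening "are less risk averse than individuals who do not" is affected. Its method may lie in the unreadable SAP 2.4.3, so nothing can be said of it.
- That the main results are biased. The equivalence values in SAP 2.5 are trade-offs within one full-cohort model, where a common scale cancels.

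**Conclusion.** The concern holds for SAP 2.3.1 as readable: the stated comparison cannot tell noisier answering from different preferences, and it is applied to a split where a noise difference is the natural expectation. With identical preferences and a 150:150 split, false findings of difference run at about 12% to 24% for a scale ratio of 0.8 and 80% to 99% for 0.5; at 270:30 and 0.8 they are 8% to 15%. These figures rest on the assumed weights, splits, ratios and joint 5% test. The direction and the remedy do not: one relative scale parameter returns the test to about its nominal level in every setting tried.

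The consequence is misinterpretation of the data-quality check and, less probably, of the scope test. The full-cohort maximum-acceptable risks are not biased by this check.

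**What to change.** - **SAP 2.3.1.** Fit the two comprehension groups jointly with a group-specific relative scale parameter (heteroscedastic conditional logit). Test equality of preferences with scale free (10 df), and report the scale ratio with its interval as the measure of response noise. Alternatively, compare scale-free ratios such as maximum-acceptable risks between the groups.
- **SAP 2.4.2.** As a safeguard, allow an arm-specific scale before comparing the 10% and 20% weights. It is identified by the four non-risk attributes, which have the same levels in both arms and contribute 2 + 3 + 1 + 1 = 7 parameters, provided that preferences for them do not depend on the risk range shown.
- **If a scale method already exists in redacted text,** cross-reference it in both sections.

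The cost is SAP wording and one extra parameter per comparison. No new data and no change to the survey are needed.
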